7.5.2 Assessment of Severity

The severity of clinical and laboratory adverse events will be assessed according to the scales in **Tables 7-10**.

Adverse Event	Grade	Intensity
Pain at injection site	1	Pain that is easily tolerated
	2	Pain that interferes with daily activity
	3	Pain that prevents daily activity
Erythema at injection site*	1	>3 - ≤ 50mm
	2	>50 - ≤100mm
	3	>100mm
Swelling at injection site*	1	>3 - ≤ 20mm
	2	>20 - ≤ 50mm
	3	>50mm
Itching at injection site	1	Itching that is easily tolerated
	2	Itching that interferes with daily activity
	3	Itching that prevents daily activity

* erythema or swelling ≤3mm is an expected consequence of skin puncture and will therefore not be considered an adverse event

Table 8:	Severity	grading	for p	hysical	observations

Adverse Event	Grade 1 (mild)	Grade 3 (severe)			
Fever (oral)	37.6°C - 38°C 38.1°C - 39°C		>39°C		
Tachycardia (bpm)*	101-115	101-115 116-130			
Bradycardia (bpm)**	50-54	40-49	<40		
Systolic Hypertension (mmHg)	141-159 160-179		≥180		
Diastolic Hypertension (mmHg)	91-99	100-109	≥110		
Systolic Hypotension (mmHg)***	85-89	80-84	<80		

*Taken after ≥10 minutes at rest

** When resting heart rate is between 60-100 beats per minute. Use clinical judgement when characterising bradycardia among some healthy subjection populations, for example, conditioned athletes.

*** Only if symptomatic (e.g. dizzy / light headed)

Table 9: Severity grading criteria for local and systemic AEs

Grade	Criteria
GRADE 0	None; Symptom not experienced
GRADE 1	Mild: Short-lived or mild symptoms; medication may be required. No limitation to usual activity
GRADE 2	Moderate: Mild to moderate limitation in activity. Medication may be required
GRADE 3	Severe: Considerable limitation in activity. Medication or medical attention required

Routine Haematology		Lab Range	Grade 0	Grade 1	Grade 2	Grade 3	
	Male		130 - 170	126 - 170	115 - 125	100 - 114	<100
Haemoglobin	Female	g/i	120 - 150	114 - 150	103 - 113	90 - 104	<90
White blood	Elevated				11.50 - 15.00	15.01 - 20.00	>20
cells	Low	x10 ⁹ /I	4.00 - 11.00	3.51 - 11.49	2.50 - 3.50	1.50 - 2.49	<1.50
Platelets		x10 ⁹ /l	150 - 400	136 - 400	125 - 135	100 - 124	<100
Neutrophils		x10 ⁹ /l	2.0 - 7.5	1.5 - 7.5	1.00 - 1.49	0.50 - 0.99	<0.50
Lymphocytes		x10 ⁹ /I	1.5 - 4.0	1.0 - 4.0	0.75 - 0.99	0.50 - 0.74	<0.50
Eosinophils		x10 ⁹ /l	0.0 - 0.5	0.0 - 0.64	0.65 - 1.50	1.51 - 5.00	>5.00
Routine Biochemistry			Lab Range	Grade 0	Grade 1	Grade 2	Grade 3
Sodium	Elevated		147 - 148	149 - 150	>150		
Low			131 -132	129 - 130	<129		
Potassium	Elevated	mmol/l	3.5 - 5.3	3.4 - 5.3	5.4 -5.5	5.6 - 5.7	>5.7
Totassium	Low	mmoi/i			3.2 - 3.3	3.0 - 3.1	<3.0
Urea		mmol/l	2.5 - 7.8	2.5 - 8.1	8.2 - 8.9	9.0 - 11	>11
Creatinine		µmol/l	53 - 97	53 - 106	1.1-1.5*ULN	>1.5-3.0*ULN	>3.0*ULN
					107 - 145	146 -291	>291
Bilirubin	Normal	umol/l	0 - 20	0 - 25	1.3-1.5*ULN	>1.5-2.0*ULN	>2.0*ULN
	LFI	F			26 - 30	31 - 40	>40
Bilirubin ^{\$}	Abnormal LFT	µmol/l	0 - 20	0 - 21	1.1-1.25*ULN	>1.25-1.5*ULN	>1.5-1.75*ULN
					22 - 25	26 - 30	>30
					1.25-2.5*ULN	>2.5-5.0*ULN	>5.0*ULN
ALT/AST	Male	IU/I	10 - 40	10 - 49	50 - 100	101 - 200	>200
	Female		7 - 35	7 - 43	44 - 87	88 - 175	>175
		IU/I	30 - 130	30 - 142	1.1-2.0*ULN	>2.0-3.0*ULN	>3.0*ULN
			00 - 100	JU - 142	143 - 260	261 -390	>390
Albumin		g/l	35 - 50	32 - 50	28 - 31	25 - 27	<25

	Table 10	: Severity	grading	criteria	for	laboratory	AEs
--	----------	------------	---------	----------	-----	------------	-----

\$ When accompanied by any increase in LFT

Coagulation studies	Lab Range	Grade 0	Grade 1	Grade 2	Grade 3
INR	0.8 - 1.2	0.8 - 1.2	1.3	1.4	≥1.5

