Appendix A: Laboratory Values for Exclusion

Laboratory parameters for inclusion/exclusion in the trial will be considered on an individual basis, with investigator discretion for interpretation of results and the need for repeated or further tests. In general, volunteers will be excluded if a result at screening constitutes what would qualify as a grade 1 (or higher) laboratory adverse event, according to the site-specific laboratory adverse event tables (filed in the TMF). Urinalysis at screening will be assessed as per the table below:

URINE ANALYSIS (using MULTISTIX)				
Protein*	2+ or Protein creatinine ratio of ≥50mg/mmol			
Blood£	2+ on two dipstick tests			
Glucose	1+			

*In the event of the dipstick testing positive for protein with $\geq 1 + \text{ protein urine should be sent for a protein creatinine ratio.}$

 ϵ In the event of urine dipstick testing positive for \geq 1+ blood with, or without, protein in volunteers a repeat dipstick test will be carried out to confirm haematuria. In female volunteers, a menstrual history will be taken to elicit whether the subject is currently menstruating and if they are, urine dipstick will be repeated after 1 - 2 weeks. If blood and/or proteinuria persist in any volunteer, an interpretation of the results will be undertaken by the investigator on an individual basis to determine if they will be excluded from the trial, and the appropriate follow-up arranged.

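### Section 7.5.2 does not give unique severity grades: female haemoglobin of 103-104 g/l falls in two bands, and some injection-site pain or itch is Grade 2 in Table 7 but Grade 3 in Table 9

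*Protocol*

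**What the plan says.** Section 7.5.2 opens with a rule that brings in all four severity tables at once: "The severity of clinical and laboratory adverse events will be assessed according to the scales in" Tables 7 to 10. It does not rank them.

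- **Table 10, haemoglobin (g/l).** Female: Grade 0 is 114-150, Grade 1 is 103-113, Grade 2 is 90-104, Grade 3 is below 90. Male: 126-170, 115-125, 100-114 and below 100.
- **Injection-site table (Table 7).** Grade 2 pain is "Pain that interferes with daily activity" and Grade 3 pain is "Pain that prevents daily activity". Itch follows the same pattern, with Grade 3 as "Itching that prevents daily activity". Erythema and swelling are graded by size.
- **Table 9.** Its title is "Severity grading criteria for local and systemic AEs". Grade 2 is "Moderate: Mild to moderate limitation in activity. Medication may be required" and Grade 3 is "Severe: Considerable limitation in activity. Medication or medical attention required".

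Section 5.3.9 (Table 4) lists warmth among the solicited local events. Warmth has no row in Table 7.

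**The concern.** A severity scale should return one grade for each finding. Here a woman with haemoglobin of 103 or 104 g/l can properly be recorded as Grade 1 or Grade 2. A volunteer whose arm pain seriously limits activity can properly be recorded as Grade 2 or Grade 3. Two assessors could each follow the protocol and disagree, and an automatic grade check in the eCRF could not be programmed for those haemoglobin values as the bands are written.

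What is at stake is the consistency of recorded severity. Severity also has a possible route into dose choice. Stage 3 expands whichever of Groups 2a and 2b has the better immunogenicity and reactogenicity profile (section 3.1), Table 1 refers to the most well tolerated dose, and section 8.1 has the investigators weigh all available tolerability information. None of these terms is defined, and severity is a natural ingredient of each.

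**Working it through.** **1. Haemoglobin (inputs from Table 10).** Count how many grade bands contain each whole-number value.

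| Row | Grade 1 | Grade 2 | Values in both |
|---|---|---|---|
| Female | 103-113 | 90-104 | 103, 104 |
| Male | 115-125 | 100-114 | none |

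The female bands overlap from the lower limit of Grade 1 (103) to the upper limit of Grade 2 (104), which is 104 - 103 + 1 = 2 values. The same check on low white cells, platelets, neutrophils, lymphocytes and albumin finds no overlap, so among the rows checked this one is the exception.

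**2. Pain and itch (inputs from Tables 7 and 9).** Take a reaction that limits daily activity considerably, needs medication or medical attention, and does not prevent activity.

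- Table 7: activity is interfered with but not prevented, so Grade 2.
- Table 9: the limitation is considerable, and medication or medical attention is needed, so Grade 3. It exceeds the mild to moderate limitation of Table 9's Grade 2.

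The need for medication does not by itself produce Grade 3, because Table 9 allows for medication at Grades 1 and 2 as well. The conflict needs both elements of Table 9's Grade 3, so the affected class is narrow.

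**3. Bilirubin with abnormal LFT (Table 10, ULN 20 µmol/l).** The row prints multiples of the ULN and absolute values:

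- 1.1 × 20 = 22, printed 22
- 1.25 × 20 = 25, printed 25
- 1.5 × 20 = 30, printed 30
- 1.75 × 20 = 35, no absolute counterpart; Grade 3 is simply above 30

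The two scales agree through Grade 2 and at the start of Grade 3. Above 35 µmol/l the absolute scale says Grade 3 and the multiple scale gives no grade. Grade 3 is the top of the table, so no competing grade exists.

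**4. Where grade is used.**

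| Element | Section | Basis |
|---|---|---|
| Primary outcomes | 2 | Occurrence of events; change from baseline in laboratory measures |
| Safety tabulation | 8.2 | Proportion with each event, and with samples outside reference ranges |
| Adaptation rules | 3.1.1 | Number with a 2-fold titre rise |
| Holding and stopping rules | 7.9.1, 7.9.2 | Seriousness and relatedness |

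None of these turns on grade. Moving an event between Grades 2 and 3 leaves its occurrence unchanged, and regrading a haemoglobin value leaves its change from baseline unchanged.

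**5. Scale, if grade does inform a judgement.** One regraded participant is 1/9 = 11.1 percentage points in Group 2a or 2b, and 1/21 = 4.8 points in the 9 + 12 = 21 participants at an expanded dose. This shows what one case would weigh. It does not forecast how many there will be.

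**The case against.** The strongest reply is that a sensible reader would use the specific row in Table 7 for pain and itch and keep Table 9 for everything else. Table 9 needs the word local in its title because warmth is solicited and has no row of its own. The caption of Table 7 is also missing from the text available for this review and might state its scope. This has force: it is probably the intended reading. But section 7.5.2 applies all the tables together and does not say so, and Table 9's title draws no line between local events with and without their own row.

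The reply also holds that Table 9's Grade 3 carries a medication or medical-attention element, so considerable limitation alone does not clearly reach it. That stands, and the conflict is confined here to reactions that meet both elements.

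Neither argument touches the haemoglobin overlap, where two bands in one row share two values.

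A reader might go further and infer that graded results are what the trial uses to compare doses. The protocol does not say this. Grade could enter only through the undefined tolerability and reactogenicity judgements, or through a summary in an analysis plan that is not shown.

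**Conclusion.** The point holds as a drafting contradiction in an operative safety-grading rule, and it is minor. Its size is two whole-number haemoglobin values in women, plus injection-site pain or itch that limits activity considerably, needs medication or medical attention, and does not prevent activity. No frequency can be given for the second class, because the protocol offers nothing from which to estimate one. The primary outcomes, the analyses in section 8.2, the responder-count rules and the holding rules are unaffected. The possible effect is on recorded severity and, through it, on the Stage 3 choice of dose.

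Two further inferences are not supported. The abnormal-LFT bilirubin row does not give two different grades; its stray upper multiple changes no grade. Nor can it be said that screening and on-study laboratory grades differ. Section 5.4.2 and Appendix A refer to site-specific tables held in the TMF, which are not available here, so no discrepancy is shown.

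The verdict assumes that haemoglobin is reported in whole g/l, that the uncaptioned injection-site table is Table 7, and that both elements of Table 9's Grade 3 must be met.

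**What to change.** - Reconcile the female Grade 1 and Grade 2 haemoglobin bands in Table 10 so that each value has one grade. The sponsor chooses the cut-off.
- State in section 7.5.2 which table governs events that have their own row in Table 7 (pain, itch, erythema, swelling), and that Table 9 applies to events without a specific row, such as warmth.
- As a tidy-up, reconcile the Grade 3 multiple for bilirubin with abnormal LFT with the absolute limit printed beneath it. This changes no grade.

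The cost is a few words in section 7.5.2 and a matching eCRF grade check. Sample size, visits and planned analyses do not change.

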7.6. Reporting procedures for AEs, SAEs and other safety events

7.6.1 Reporting Procedures for AEs

All AEs occurring in the 28 days following each vaccination observed by the Investigator or reported by the volunteer, whether or not attributed to study medication, will be recorded. AEs deemed to be not serious by the investigator will be recorded in the site's AE log and on the eCRF by the study team within 5 days of the study visit. AE data will be made available to the LSC before each interim safety analysis.

7.6.2 Reporting Procedures for SAEs

Serious adverse events (SAEs) will be collected throughout the entire trial period. In order to comply with current regulations on serious adverse event reporting to regulatory authorities, the event will be documented accurately and notification deadlines respected. SAEs will be reported on the SAE forms by members of the study team immediately after the Investigators become aware of their occurrence. Copies of all reports will be forwarded for review to the Chief Investigator or delegated investigator and the Sponsor's representative ([contact]) within 24 hours of the Investigator being aware of the suspected SAE. The local safety committee (LSC) will be notified of SAEs which are deemed possibly, probably or definitely related to study interventions; the LSC will be notified immediately (within 24 hours) of the Investigators' being aware of their occurrence by the Chief Investigator or delegated member of the study team. A copy of the SAE report will be sent to them for information and safety review purposes only; the LSC are not responsible for reporting of SAEs. SAEs will not normally be reported immediately to the REC unless there is a clinically important increase in occurrence rate, an unexpected outcome, or a new event that is likely to affect safety of trial volunteers, at the discretion of the Chief Investigator and/or LSC. In addition to the expedited reporting above, the Investigator shall include all SAEs in the annual Development Safety Update Report (DSUR) report.

7.6.3 Reporting Procedures for SUSARS

The sponsor will report all SUSARs to the MHRA and REC within required timelines (15 days for all SUSARs, unless resulting in death or is life threatening in which case 7 days, with a final report within a further 8 days (total 15)). The Chief Investigator will also inform all Investigators concerned of relevant information about SUSARs that could adversely affect the safety of participants.

All SUSARs and deaths occurring during the study will be reported to the Sponsor by the investigator by emailing [contact]. For all deaths, available autopsy reports and relevant medical reports will be made available for reporting to the relevant authorities.

7.6.4 Development Safety Update Report

A Development Safety Update Report (DSUR) will be submitted by the Sponsor to the competent authority and ethics committee on the anniversary of the first approval date from the regulatory authority for the IMP.

7.6.5 Pregnancy Reporting

Volunteers that are pregnant or plan on becoming pregnant during the course of the study will not be enrolled.

Should a volunteer become pregnant during the trial, she will not receive any further investigational medicinal product and will be followed up as other volunteers and in addition will be followed until pregnancy outcome, with the volunteer's permission. We will not routinely perform venepuncture on such volunteers.

If a female subject or a female partner of a male subject becomes pregnant at any point during the trial, a completed trial specific Pregnancy Report must be submitted to the sponsor ([contact]) within 1 business day of learning of its occurrence.

Table 11: Reporting periods for collecting safety information

	Screening	Day 0 Vaccine 1	Day 1 T/C	Day 3	Day 7	Day 14	Day 28 Vaccine 2	Day 42	Day 56	Day 84	Day 182	Day 365
Attendance number	1	2	3	4	5	6	7	8	9	10	11	12
Solicited local and systemic AEs												
Unsolicited AEs												
AEs/SAEs leading to withdrawal from the study			-				-					
SAEs (including adverse events of special interest)												
SAEs related to study participation (starting from provision of informed consent)												
Pregnancy (♀)												

7.7. Follow-up of AEs and SAEs

7.7.1. Follow-up during the study

In the event of AE's occurring during the study period appropriate follow-up visits or medical care will be arranged, with the agreement of the volunteer, until the AE has resolved, stabilised or a non-trial related causality has been assigned.

7.7.2. Follow-up after the volunteer is discharged from the study

AEs that result in a volunteer's withdrawal from the study or that are present at the end of the study will be followed up (if the volunteer consents to this) until a satisfactory resolution or stabilisation occurs, or until a non-study related causality is assigned. All AEs/SAEs leading to withdrawal from the study will be collected and recorded from the time of the first receipt of pEVAC-PS.

7.8. Procedures to be followed in the event of abnormal findings

Eligibility for enrolment in the trial in terms of laboratory findings will be assessed as detailed in Appendix A. Abnormal clinical findings from medical history, examination or blood tests will be assessed as to their clinical significance throughout the trial. Laboratory adverse events will be assessed using the details in Table 10. If a test is deemed clinically significant, it may be repeated to ensure it is not a single occurrence. If a test remains clinically significant, the volunteer will be informed, and appropriate medical care arranged as appropriate and with the permission of the volunteer. Decisions to exclude the volunteer from enrolling in the trial or to withdraw a volunteer from the trial will be at the discretion of the Investigator.

7.9. Safety Stopping/ Holding Rules

Safety holding rules have been developed considering the fact that this is a first-in-human dose escalation study. Safety reviews will take place prior to each dose escalation as referenced in **Section 3.5**.

7.9.1. Group Holding Rules

The following holding rules will apply to all study groups. If a holding rule is activated, then further vaccinations will not occur until an internal safety review has been conducted by the LSC and it is deemed appropriate to restart dosing. All other procedures relating to safety and immunology will continue. The regulatory authority must be informed of the activation of any holding rule and a request to restart dosing with pertinent data must be submitted as a request for a substantial amendment. The internal safety review will consider:

• The relationship of the AE or SAE to the vaccine.

- The relationship of the AE or SAE to the vaccine dose, or other possible causes of the event.
- If appropriate, additional screening or laboratory testing for other volunteers to identify those who may develop similar symptoms and alterations to the current Participant Information Sheet (PIS) are discussed.
- New, relevant safety information from ongoing research programmes on the various components of the vaccine.

The Research Ethics Committee and IMP manufacturer will also be notified if a holding rule is activated or released. All vaccinated volunteers will be followed for safety until resolution or stabilisation (if determined to be chronic sequelae) of their AEs.

The group holding rules are as follows:

- One serious event considered by the investigator to be at least possibly related to the study drug
- Two serious adverse reactions considered by the investigator to be at least possible related to the study drug, irrespective of duration and whether the reactions are the same or not

These rules apply to both solicited and non-solicited adverse events as well as to laboratory adverse events.

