- An important medical event (that may not cause death, be life threatening, or require hospitalisation) that may, based upon appropriate medical judgment, jeopardise the volunteer and/or require medical or surgical intervention to prevent one of the outcomes listed above. Examples of such medical events include allergic reaction requiring intensive treatment in an emergency room or clinic, blood dyscrasias, or convulsions that do not result in inpatient hospitalisation.
- Congenital anomaly or birth defect.

Serious Adverse Reaction (SAR)

An adverse event that is both serious and, in the opinion of the reporting investigator or sponsor, believed to be possibly, probably or definitely due to the inoculum or any other study treatments, based on the information provided in the protocol.

Suspected Unexpected Serious Adverse Reactions (SUSARs)

A SUSAR is a SAE that thought to be possibly, probably or definitely related to the inoculum and is unexpected in nature (when assessed against the IB).

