7.9.2. Individual Stopping Rules

In addition to the above stated group holding rules, stopping rules will apply for individual volunteers in the occurrence of a serious adverse event considered by the investigator to be at least possibly related to the study drug. This applies to both solicited and unsolicited events as well as to laboratory parameters.

In addition to these pre-defined criteria, the study can be put on hold upon advice of the Chief Investigator, Study Sponsor, regulatory authority, Research Ethics Committee (REC) or Local Safety Committee (LSC), for any single event or combination of multiple events which, in their professional opinion, jeopardise the safety of the volunteers or the reliability of the data.

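### Group holding Rule 2 can never fire without Rule 1, and no pre-defined rule uses a severity grade, so a cluster of related grade 3 non-serious reactions meets no pre-set holding criterion

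*Protocol*

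**What the plan says.** Protocol section 7.9.1 lists two group holding rules. Rule 1: "One serious event considered by the investigator to be at least possibly related to the study drug". Rule 2: "Two serious adverse reactions considered by the investigator to be at least possible related to the study drug", with the qualifier that neither duration nor similarity of the reactions matters. On scope it adds: "These rules apply to both solicited and non-solicited adverse events as well as to laboratory adverse events".

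Section 7.1 defines a serious adverse reaction as "An adverse event that is both serious and, in the opinion of the reporting investigator or sponsor", at least possibly due to the study product. Seriousness is defined there by outcome, such as death, threat to life, disability or hospitalisation. Severity is graded separately, 1 to 3, in Tables 7 to 10 (section 7.5.2).

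The individual stopping rule in 7.9.2 applies "in the occurrence of a serious adverse event considered by the investigator to be at least possibly related to the study drug".

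Escalation depends on these rules. Sections 3.1 and 3.5 let the next dose level open after a 72-hour review if no stopping criterion in 7.9 has been met. Section 8.1 also refers dose-adaptation decisions to the 7.9 stopping rules.

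The protocol also provides for judgement. Section 7.9 states: "Safety reviews will take place prior to each dose escalation". Section 7.6.1 states: "AE data will be made available to the LSC before each interim safety analysis". Sections 7.9.2 and 7.10 allow the study to be put on hold "for any single event or combination of multiple events which, in their professional opinion, jeopardise the safety of the volunteers".

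**The concern.** Two rules that differ only in needing one or two events of the same kind are in effect one rule. The second should catch something that the first does not, and as written it catches nothing.

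The natural candidate for a second rule is severity. Section 7.9.1 extends the rules to solicited and laboratory events, which Tables 7 to 10 grade, yet no rule names a grade. In Table 9 a grade 3 event markedly restricts activity and needs medication or medical care. Several participants at one dose could have such reactions, judged related, without any of them being serious.

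At stake is whether the protocol says in advance what happens then. Without a stated threshold, the people running an open-label escalation decide case by case whether a given number of severe reactions should stop the next dose level from opening.

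**Working it through.** The protocol states no operating characteristic for the holding rules, so there is no figure to reproduce. The check is logical first, then an illustration of size.

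**Step 1: containment.** Let *s* be the number of at least possibly related serious events and *g* the number of related grade 3 non-serious reactions.
- Rule 1 (7.9.1) fires if *s* ≥ 1.
- Rule 2 (7.9.1) fires if *s* ≥ 2, because under 7.1 each serious adverse reaction is both serious and related. The definition in 7.1 also admits the sponsor's opinion on relatedness, but Rule 2 itself requires the investigator's attribution, as Rule 1 does.
- *s* ≥ 2 implies *s* ≥ 1. Over *s* = 0 to 9 and *g* = 0 to 9 (100 states), Rule 2 fires without Rule 1 in 0 states.
- After a hold is released, the next related serious event meets Rule 1 again, so order in time does not rescue Rule 2.

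**Step 2: severity.** *g* appears in none of the three pre-defined rules (two group, one individual). With *s* = 0, no rule fires for any *g* from 0 to 9. The scope sentence in 7.9.1 widens the type of event but does not remove the word serious.

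**Step 3: how often the question could arise.** Let *p* be the true proportion of participants with a related grade 3 non-serious reaction. The protocol gives no value, so *p* is assumed, and taken as equal at every dose. For a group of *n*:

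P(X ≥ 2) = 1 − (1 − p)^n − n·p·(1 − p)^(n−1)

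For example, n = 6 and p = 0.10: 1 − 0.531 − 0.354 = 0.114 (before rounding of the terms).

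| Assumed p | n = 6 | n = 9 | n = 12 |
|---|---|---|---|
| 2% | 0.006 | 0.013 | 0.023 |
| 5% | 0.033 | 0.071 | 0.118 |
| 10% | 0.114 | 0.225 | 0.341 |
| 20% | 0.345 | 0.564 | 0.725 |

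Under the rules as written, the probability that such events meet a pre-defined criterion is 0 in every cell.

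**Step 4: holds under a severity trigger of two per group, with no duration limit.** For groups of 6, 9, 9 and 12 (36 in total), counted separately and independent:

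P(at least one hold) = 1 − (1 − P6)(1 − P9)²(1 − P12)

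- p = 2%: 0.054
- p = 5%: 1 − 0.967 × 0.929² × 0.882 = 0.264
- p = 10%: 1 − 0.886 × 0.775² × 0.659 = 0.650
- p = 20%: 0.966

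The order 6, 12, 9, 9 gives the same result.

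**The case against.** The strongest reply is that a severe cluster would not pass unseen.
- Significant concerns during post-vaccination observation go to the chief investigator and local safety monitor (5.5.1).
- An extra clinical review is considered for moderate or severe symptoms (7.13).
- Safety reviews precede each escalation (7.9), and the local safety committee receives AE data (7.6.1) and issues a decision on monitored data (7.12).
- Adaptation decisions use all tolerability information available, with safety data fully source-verified (8.1).
- Anyone with oversight may call a hold (7.9.2, 7.10).
- Some grade 3 events could reach Rule 1 as events of special interest (7.4) or important medical events (7.1).

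The committee's terms of reference, which set the content of its safety reports, are not at hand. There is also one site and one committee, which favours consistent decisions.

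All of this stands, and it limits the point. A reader might infer that dosing would simply continue through a severe cluster; the documents do not support that, because review before escalation is required and a discretionary hold is always open. What these routes lack is a stated threshold, and 7.9.2 itself separates discretionary holds from the pre-defined criteria. The 24-hour notification of the committee covers only related serious events (7.6.2, 7.10), so a severe non-serious cluster has no automatic immediate route to it.

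A second reply is that Rule 2 may contain a slip, with serious written for severe. Its indifference to duration and to similarity of reactions would suit a severity rule. That is plausible but is inference; the protocol does not say it, and the point does not depend on it.

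**Conclusion.** The point holds and should be fixed. Rule 2 is inoperative as written, and none of the three pre-defined rules uses a severity grade. Two of 6, three of 9 or all participants in a group could have related grade 3 non-serious reactions without meeting a pre-set criterion at the 72-hour gates. These conclusions follow from the text and need no assumption.

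The size is less certain. The probabilities rest on assumed rates of 2% to 20%, equal across doses, with independent participants. They show how often the question would come up. A reader might take them as the chance that dosing wrongly continues; they are not, because judgement may well stop it. Nor does the point reach related serious events: Rule 1 holds dosing at the first one.

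**What to change.** Reword Rule 2 as a severity trigger and keep its existing qualifier. For example: dosing is held if two or more participants in a group have a severe (grade 3) adverse reaction judged at least possibly related to the study drug, whatever its duration and whether or not the reactions are alike. The sponsor should confirm whether severe was intended in place of serious. The sponsor and the local safety committee may choose a different count, or a duration limit for solicited reactions. The 72-hour gates need no separate change, since they already refer to section 7.9.

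The wording change is cheap; the holds are not. Each needs committee review and a substantial amendment before restart (7.9.1), with a response within 35 days of the notice (11.9), so about five weeks. With no duration limit, the chance of at least one hold over the 36-participant path is about 5%, 26%, 65% and 97% at assumed grade 3 rates of 2%, 5%, 10% and 20%. A duration limit would lower these figures, by an amount that depends on the unknown mix of solicited and other events. If the sponsor expects grade 3 reactions to be common, the count and any duration limit should be chosen with these figures in view.
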